The spinal cord relies on input from the motor cortex as well as sensory information from the extremities to carry out specific actions. For example, recent evidence suggests that preservation of temporally specific proprioceptive information via dorsal column primary afferent fibers is critical for motor behaviors such as ambulation. Since the spinal cord is exposed during the placement of the SCS device, information about a subject's motor and sensory spinal pathways can be easily obtained during the regular course of the procedure and compared to proprioceptive and motor responses once the subject is awake and moving with the device turned on. Our lab specializes in electrophysiological recordings in subjects undergoing spinal cord stimulator (SCS) implantation for CLBLP, while MUSC's Locomotion Laboratory specializes in quantifying proprioception and movement in human subjects. In this proposal, we will apply these techniques to subjects with CLBLP to determine effects of spinal neuromodulation on motor and sensory thresholds, proprioception, and kinematics. Our plan includes the following specific aims:

**Aim 1. Compare the effects of LFTS and HFBS on motor and sensory thresholds intraoperatively.** Question: Do HFBS waveform patterns modulate motor and sensory thresholds to allow more information to reach the spinal cord? In this aim, we will measure sensory and motor spinal thresholds in subjects undergoing SCS implantation during stimulation of epidural paddle contacts. *We hypothesize that HFBS will reduce motor and sensory thresholds relative to LFTS during epidural paddle activation.*

**Aim 2. Determine the effect of HFBS on proprioceptive afferent signaling from lower extremity muscle groups.** Question: Does HFBS, when compared to traditional LFTS, allow for increased spatial limb awareness during passive motion? In this aim, postoperative subjects from SA1 will undergo isokinetic passive proprioceptive testing before, during and after spinal cord stimulation with HFBS and LFTS parameters targeting musculature surrounding the knee. *We hypothesize that subjects will have increased awareness of the lower limb in space through passive movement during optimal HFBS compared to optimal LFTS parameters.*

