**Aim 3. Determine the effect of HFBS on lower extremity musculature during gait.** Question: Does HFBS, when compared to LFTS, differentially affect muscle synergy patterns during gait? In this aim, subjects from SA1 and SA2 will perform treadmill walking before, during and after SCS stimulation. Subjects will be monitored with surface EMG and 3-D kinematic tracking software to quantify any changes in walking pattern. *We hypothesize that subjects will have increased EMG module complexity during gait while experiencing optimal HFBS compared to optimal LFTS or no stimulation.*

Date: 8/1/19

Version: 01

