#### **5.0 Number of Subjects**

We propose to study 5 individuals with CLBLP. A prior study conducted by Formento et al, 2018 using SCS and proprioceptive testing published a standard error and 95% confidence interval using successful and unsuccessful SCS trial attempts ( $p < 0.05$  among LFTS parameters and no stimulation, with a minimum of 10 trials per stimulation setting). Based on this, we expect that our small population will exhibit similar variance. The subject sample size is in direct comparison to sample sizes of previous proof of concept studies regarding SCS for spinal cord physiology biomarker sampling. The research team plans to use a two-way repeated measures ANOVA model in order to investigate the varying differences in stimulation type and kinematic parameters. A Post hoc comparison will be made using a Tukey adjustment.

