### **Step 2: Proprioception testing before, during and after SCS stimulation**

All of the following are for research purposes and not considered standard of care for SCS surgery. Following an approximately 30-day recovery period from surgical placement of the paddle and IPG, subjects will undergo

Date: 8/1/19

Version: 01

stimulation configuration mapping (SCM) in the Locomotor Rehabilitation Laboratory at the College of Health Professions Building C at MUSC in order to determine electrode and parameter configurations that elicit activation of lower extremity musculature. For this testing, we will place surface EMG pads on subjects' skin overlying muscles of interest. Using the Boston Scientific external stimulator interface, we will wirelessly activate the implanted spinal paddle and compare muscle activation using LFTS and HFBS patterns by systematically testing each individual contact. Subjects will comfortably lie supine on a large, low-rise rehabilitation mat common to any physical rehabilitation clinic during SCM.

Next, we will investigate the perceived change in knee joint angle and direction of movement reported by the subject in a Threshold to Detect Passive Movement (TTDPM) task. The TTDPM protocol will begin with the subject sitting in the Biodex testing seat, with the non-tested leg hanging freely and the tested leg strapped to the rotating arm of the dynamometer at the lower shank. The subject will be blinded as to the mode and intensity of stimulation: HFBS, LFTS, or no stimulation. Furthermore, in order to shield the subject from witnessing initiation, direction and approximate distance traveled of the shank, the subject will be asked to wear a blindfold and headphones playing a soft background noise (Figure 3). The TTDPM will consist of at least 10 trials for each stimulation condition. The subject has control of a switch that immediately halts movement of the rotating arm, which is to be activated once the subject perceives movement **OR** if the subject begins to feel any pain or discomfort throughout the task. Our research team anticipates data collection to last approximately 3 hours per subject for this step (1 hour for supine SCM, 1 hour for TTDPM and 1 hour for set up and breakdown). Proprioception testing will take place before, during and after SCS stimulation.

Figure 3: TTDPM test using a Biodex

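### No aim randomises or balances the order of HFBS and LFTS, so a shared time trend could enter the main within-subject contrast

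*Combined protocol and SAP*

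**What the plan says.** Section 5.0 plans 5 subjects, and section 1.0 uses the same people in every aim. Aim 1 contrasts motor and sensory thresholds under HFBS and LFTS during surgery. In Aim 2 those subjects "will undergo isokinetic passive proprioceptive testing before, during and after spinal cord stimulation with HFBS and LFTS parameters". In Aim 3 they walk on a treadmill, and the hypothesis concerns EMG module complexity "while experiencing optimal HFBS compared to optimal LFTS or no stimulation".

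Section 9.0 gives the conduct:

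- **Step 1.** Both patterns are activated in the same operation. The list of research procedures points to the study protocol for the patterns and allows about 15 minutes.
- **Step 2.** On the threshold to detect passive movement (TTDPM) task: "The subject will be blinded as to the mode and intensity of stimulation: HFBS, LFTS, or no stimulation". On quantity: "The TTDPM will consist of at least 10 trials for each stimulation condition". On timing: "Proprioception testing will take place before, during and after SCS stimulation". The session is split into "1 hour for supine SCM, 1 hour for TTDPM and 1 hour for set up and breakdown".
- **Step 3.** The two patterns are compared contact by contact during walking, with practice beforehand, a run-in of about 10 seconds per trial and rest as needed.

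For analysis, section 5.0 names a "two-way repeated measures ANOVA model in order to investigate the varying differences in stimulation type and kinematic parameters", and then: "A Post hoc comparison will be made using a Tukey adjustment".

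None of these places says which pattern is given first, whether trials are blocked or interleaved, or whether order is randomised or balanced.

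**The concern.** In a within-subject comparison, the order of conditions does the work that allocation does in a parallel-group trial. The plan's own schedule makes time trends plausible: about 15 minutes of testing under general anaesthesia in Step 1, an hour of TTDPM allotted alongside an hour of mapping in Step 2, and repeated treadmill trials in Step 3.

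If every subject receives the patterns as blocks in the same order, a trend that subjects share is added to HFBS minus LFTS. More trials or more subjects in that order would estimate the shifted value more precisely without removing the shift. An ANOVA with stimulation type but no time term credits it to the pattern.

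The Step 2 timing sentence does not settle the matter. It places off testing around stimulation and does not order one pattern against the other. The off trials could bracket each pattern or the whole session. It is also not stated whether they are the same trials as the blinded no-stimulation condition of the TTDPM task.

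**Working it through.** The plan gives no figure to reproduce: there is no drift size, SD, effect size or power calculation. What follows is illustration on stated assumptions.

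**Inputs from the documents:** 5 subjects (section 5.0); at least 10 TTDPM trials per condition and three conditions (Step 2); repeated measures ANOVA with Tukey comparisons (section 5.0).

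**Assumed:** linear drift of b per trial, shared by all subjects, with trials numbered from 0. The shift in HFBS minus LFTS is then b × (mean HFBS position − mean LFTS position).

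1. *One common order, LFTS block then HFBS block.* LFTS takes positions 0–9 (mean 4.5) and HFBS 10–19 (mean 14.5). Shift = (14.5 − 4.5)b = **10b**. Putting 5 off trials before and 5 after the pair gives means of 9.5 and 19.5, again 10b.
2. *Strict alternation, LFTS first.* LFTS takes 0, 2, …, 18 (mean 9) and HFBS 1, 3, …, 19 (mean 10). Shift = **1b**.
3. *Mirrored order A-B-C-C-B-A, 5-trial blocks, 30 trials.* Mean positions are A (2 + 27)/2, B (7 + 22)/2 and C (12 + 17)/2, each 14.5. Shift = **0** for every pair. This cancels linear drift only.
4. *Off blocks of 5 around each pattern, middle block shared.* LFTS takes 5–14 (mean 9.5) and HFBS 20–29 (mean 24.5), so the raw shift is 15b. The off blocks average (2 + 17)/2 = 9.5 around LFTS and (17 + 32)/2 = 24.5 around HFBS, so change from the bracket has shift 0. With independent trial errors of variance s², the direct difference has variance 2s²/10 = 0.2s². The bracketed one has 0.2s² + (1/4)(2s²/5) = 0.3s², which is 1.5 times as large. The plan does not state this analysis.

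**Effect on false positives under one common order.** Let d be the shift divided by the SD of the within-subject difference, with no true pattern effect. The noncentrality is d√5.

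- Tukey, three conditions, sphericity assumed: error df = (3 − 1)(5 − 1) = 8, and critical t = 4.041/√2 = 2.857.
- Paired t-test (assumed, two-sided 5%): df = 4.

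| d | Tukey, HFBS–LFTS | Paired t |
|---|---|---|
| 0 | 2.1% | 5.0% |
| 0.25 | 3.6% | 7.2% |
| 0.5 | 8.8% | 14.1% |
| 1 | 33.4% | 40.1% |

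The values of d are arbitrary and cannot be tied to b without an SD. No size is derived for Aims 1 and 3.

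**The case against.** The strongest reply is that the documents never say one common order will be used. Blinding the subject to mode is compatible with interleaving. Testing contact by contact is compatible with giving both patterns at each contact, and under strict alternation the shift is about 1b, not 10b. The blindfold and headphones, treadmill practice, run-in and rest may also reduce time effects. Finally, Aim 2 can be read as off testing around each pattern, and change from such a bracket removes linear drift even in a common order.

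Much of this stands. It limits the point to a possible bias, and it rules out saying that no later analysis could recover the contrast. It does not close the gap. Blinding addresses expectation and cues rather than time. Practice and rest may lessen a trend but do not balance it. The bracketed analysis is neither stated nor clearly supported by the schedule, and interleaving, if intended, is not recorded.

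It is also fair to say that an elaborate scheme of orders would be out of proportion in a five-subject proof-of-concept study. Stating that order is randomised or counterbalanced closes the main gap.

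**Conclusion.** The point holds as a design omission. The order of HFBS and LFTS is uncontrolled on paper in all three aims, and the stated ANOVA has no term for time. Under one common blocked order with 10 trials per pattern and linear drift, the HFBS–LFTS contrast moves by 10b, against about 1b if alternated and 0 if mirrored. How large b is, and whether it differs from zero, cannot be learned from the documents.

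Three stronger readings are tempting and are not supported:

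- *The contrast will be biased.* This needs both a common order and a shared trend, and the documents establish neither.
- *The off trials in Step 2 leave Aim 3 without a clear comparator.* Step 2 is the TTDPM task for Aim 2. Aim 3's no-stimulation comparison comes from walking in Step 3. The ambiguity over off trials in Step 2 concerns Aim 2 only.
- *A stimulation-off interval between patterns is required.* No section documents carry-over. Such an interval is optional.

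The change should be made before the first subject is tested, because a shared order cannot be reliably repaired afterwards.

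**What to change.** Before the first subject, prepare a randomised order list and describe it in section 9.0.

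- **Step 2:** randomise or mirror the HFBS, LFTS and no-stimulation TTDPM blocks within each subject, for example A-B-C-C-B-A in blocks of 5. This keeps at least 10 trials per condition. Vary the starting order at random across subjects.
- **Step 3:** randomise or mirror the LFTS, HFBS and off walking trials within subject.
- **Step 1:** randomise or alternate which pattern is tested first, within the existing 15 minutes or so.
- **Analysis (section 5.0):** record trial order. If a time term is wanted, fit it in a trial-level mixed model. Under a mirrored order all conditions share one mean position, so a linear term cannot be estimated from condition means.
- **Step 2 wording:** state whether the before and after trials bracket each pattern or the session, and whether they are also the blinded no-stimulation condition.

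Any stimulation-off interval, and its length, is for the clinical team.

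The cost is a one-page list and a few more changes of condition per session, with no added subjects and no added surgical time. Only two of the six mirrored orders begin and end with off trials. If the before and after trials are kept separately, about 10 more may be needed (5 + 5, so 30 becomes 40) within the hour allotted to TTDPM. The extra changes in Step 3 must fit the hour shared by walking mapping and gait analysis. They cannot be costed because the number of walking trials is not given.

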### Step 3: Body weight support and treadmill (BWST) testing before, during and after SCS stimulation

Figure 4:  
Demonstration of treadmill walking while undergoing 3-D kinematic tracking and EMG capture.

All of the following are for research purposes and not considered standard of care for SCS surgery. The following methods for gait and EMG module analysis have been developed and extensively tested by MUSC researchers at the College of Health Professions. Similar to step 2, LFTS and HFBS patterns will be compared by systematically testing each individual contact on the paddle while investigating for changes in stepping speed, pattern and EMG modulating complexity. Regarding EMG module analysis, muscle activity will be recorded bilaterally via surface EMG from the medial gastrocnemius, soleus, tibialis anterior, rectus femoris, vastus medialis, biceps femoris, semimembranosus and gluteus medius. Furthermore, subjects will also have active LED markers placed over their clothes in order to track whole body kinematics throughout this portion of the study.

First, subjects will walk across a GAITRite mat (CIR Systems, Franklin, NJ) to measure self-selected overground walking speed and other spatiotemporal gait parameters. Subjects will then be permitted to practice walking on the Instrumental Treadmill until they feel comfortable. To optimize capture of steady state data on the treadmill, each subject will walk for approximately 10 sec prior to the 30 sec of data collection (40 sec per trial). This will allow capture of at least 10 consecutive steady state gait cycles (depending on cadence) per each amplitude selection for each stimulation delivery technique, which will be defined by parameters found during walking SCM. We will allow as much rest as needed between trials. For all trials, subjects will wear their own low-heeled shoes. A safety harness (Robertson Mountaineering, Fort Collins, CO) mounted to the laboratory ceiling will be worn by the participant to protect them in the event of loss of balance. Our research team anticipates data collection to last approximately 2 hours per subject for this step (1 hour for walking SCM and gait analysis and 1 hour for set up and breakdown). For their participation in step 2 and step 3 of the study, participants will be

Date: 8/1/19

Version: 01

remunerated \$50.00 in the form of a check (\$10.00 for lunch reimbursement and \$40.00 for completion of steps 2 and 3).

Through EMG capture and high/low bandpass filtering to extinguish biologic artifact and equipment artifact respectively, segments of EMG that were recorded through functional task can be analyzed with an algorithm that yields hierarchical complexities representative of muscle synergies. The research team will use previously outlined methodology to define modules through non-negative matrix factorization, where analysis will be applied to consecutive gait cycles.

The Instrumental Treadmill (Bertec, Scotland, U.K), GAITRite mat (CIR Systems, Franklin, NJ), motion capture system (PhaseSpace, San Leandro, CA), and MA300 EMG system (Motion Labs, Baton Rouge, LA) have been used in the same manner described above in the following MUSC IRB approved protocols: **Pro00028941**, Assessment of contributions to impaired walking after neurologic injury; **Pro00088728**, Fatigue and mobility in stroke: a biomechanical and neurophysiological investigation; **Pro00048394**, The effects of impaired post-stroke coordination and motor pathway integrity on mobility performance; **Pro00059390**, A novel mechanics-based intervention to improve post-stroke gait stability.

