#### **Overground and Treadmill Walking**

Subjects will be asked to walk on a pressure sensitive mat at self-selected walking speeds and on a treadmill at self-selected walking speeds with each scenario having the subject in an upper thoracic safety harness which is tethered to the ceiling for fall protection. Despite the aforementioned safety measures, there still exists a risk of loss of balance, fall and potential injury. The risk to subjects through these tasks do not exceed risks involved with general physical therapy settings and may result in mild muscle fatigue or discomfort that generally subsides within a few days. Subjects will be given ample rest time and may have additional rest time at any point throughout data collection periods. Furthermore, subjects will be assisted during large movements or during potential transfers across different surfaces by an IRB-approved study member.

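### Motion-capture markers go over subjects' clothes with no fixation or close-fitting garment required, so garment shift between trials could add avoidable error to the marker-derived kinematics with n = 5

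*Combined protocol and SAP*

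**What the plan says.** Section 9.0, Step 3 says that "subjects will also have active LED markers placed over their clothes in order to track whole body kinematics throughout this portion of the study". In the same step a harness "mounted to the laboratory ceiling will be worn by the participant to protect them in the event of loss of balance", and section 13.0 describes it as an "upper thoracic safety harness which is tethered to the ceiling for fall protection". Each treadmill trial lasts 40 seconds, of which 30 are recorded, giving at least ten gait cycles per setting. Subjects may rest between trials for as long as they like. Nothing is said about the type of clothing, how markers are secured, a static reference, re-calibration between conditions, or the order in which LFTS and HFBS are walked.

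Kinematics enter the analysis in two places. Under Aim 3 (section 1.0), "Subjects will be monitored with surface EMG and 3-D kinematic tracking software to quantify any changes in walking pattern". Section 5.0 proposes 5 subjects and names a single model, a "two-way repeated measures ANOVA model in order to investigate the varying differences in stimulation type and kinematic parameters", followed by "A Post hoc comparison will be made using a Tukey adjustment". It does not define the kinematic parameters.

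**The concern.** A marker on cloth follows the cloth, not the limb beneath it. If it sits in the wrong place by the same amount all session, the error cancels in a within-subject HFBS-LFTS difference, at least for linear measures. If the garment moves between trials, for example when the subject sits to rest, the error does not cancel. Every gait cycle in a trial shares that displacement, so averaging ten or more cycles does not remove it.

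The error would fall on the outcomes tied to the only named model. With five subjects there is little precision to spare, and data from five surgical patients are hard to collect again.

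**Working it through.** **The plan's own figure.** N = 5 cannot be reproduced. Section 5.0 gives no effect size, SD or target power. It appeals to similar variance in a cited study and to the sample sizes of earlier proof-of-concept work. The documents also give no marker error and no SD for any kinematic measure, so what follows is illustrative.

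**Inputs.** From the documents: n = 5, with each subject measured under each condition. Assumed: a 40 cm limb segment; a marker at one end shifting 0.5, 1 or 2 cm perpendicular to the segment and in the measured plane; one independent shift per condition; a paired HFBS-LFTS difference with SD of 2 or 3 degrees before marker error.

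**Formulas.**
- Angle error per condition: e = arctan(shift / 40 cm), which gives 0.72, 1.43 and 2.86 degrees.
- SD of the difference: sqrt(base² + 2e²), because each of the two conditions carries its own error.
- 95% half-width: 2.776 × SD / sqrt(5) = 1.242 × SD, where 2.776 is the t quantile on 4 df.

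For example, with base SD 2 and a 1 cm shift, SD = sqrt(4 + 2 × 1.43²) = 2.84. The half-width is 1.242 × 2.84 = 3.53 degrees, against 2.48 with no marker error, so the interval is 42% wider.

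| Shift (cm) | e (degrees) | Half-width, base SD 2 | Wider by | Half-width, base SD 3 | Wider by |
|---|---|---|---|---|---|
| 0 | 0 | 2.48 | – | 3.72 | – |
| 0.5 | 0.72 | 2.79 | 12% | 3.93 | 6% |
| 1 | 1.43 | 3.53 | 42% | 4.49 | 21% |
| 2 | 2.86 | 5.60 | 126% | 6.25 | 68% |

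**Sensitivity to the assumptions.** Cloth sliding along the limb produces almost no angle error. If shifts were independent between trials and four trials per condition were averaged (an assumption), e = 1.43 would fall to 1.43 / sqrt(4) = 0.72, and the 42% widening at base SD 2 would fall to 12%. The table is therefore close to an upper bound for these shift sizes.

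**A check that does not use joint angles.** Let r be the marker-error variance divided by the error-free variance of the paired difference, so that the SD is multiplied by sqrt(1 + r). For r from 0.10 to 1.00 the interval widens by 5% to 41%. For an unadjusted paired t test at an assumed two-sided 5% level with n = 5, 80% power needs a standardised paired difference of about 1.68. Over the same range of r that power falls to between 76% and 52%. The planned ANOVA with Tukey adjustment would give different absolute values.

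**The case against.** **Shift is inferred.** The documents do not say that garments are loose or that markers move, and clothing can be close-fitting. The photograph that goes with Step 3 is not available to this review and may show the set-up. The protocol says its gait and EMG methods were tested at length locally, and it lists other approved protocols that used the same motion-capture equipment. This stands as a limit on what can be claimed. It does not remove the point, because neither statement gives a fixation rule or an error figure.

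**The affected outcomes are limited.** The Aim 3 hypothesis concerns EMG module complexity, obtained from surface EMG by non-negative matrix factorization. Overground speed and spatiotemporal measures come from the GAITRite mat. No joint angle during gait is named as an outcome. All of this stands. The point reaches only marker-derived kinematics, and joint angle serves above as an example.

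**The harness argument is weak for the legs.** An upper thoracic harness is more likely to disturb trunk markers than leg markers. This also stands, although leg garments can shift without any pull from the harness.

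**Bias is not shown.** A reader might infer that over-clothing markers bias the HFBS-LFTS comparison. That would need drift that follows condition, for example one pattern always walked later. The documents do not state the order, so bias is neither shown nor excluded. Recordings before and after stimulation bracket the session and give a partial check on drift, though they would not locate a shift between two particular trials.

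**Conclusion.** The point holds as a minor one about measurement precision. As written, the placement allows an avoidable error source into the marker-derived kinematics, and that error could widen the HFBS-LFTS contrast. Its size cannot be established from the documents. The range of about 6% to 126% rests wholly on the assumed segment length, shift size and direction, one independent shift per condition, and a paired SD of 2 to 3 degrees.

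The documents do not support two stronger readings: that clothing shift does distort the kinematic results, and that it undermines Aim 3. The first treats an inference as fact, and the second overlooks that the hypothesis outcome does not depend on marker position.

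**What to change.** In section 9.0, Step 3, replace the over-clothing placement with placement on skin, on close-fitting garments or on strapped segment clusters. Surface EMG already needs electrode access at eight muscles per leg, so the extra burden is small.

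Optionally, add a brief static standing capture with stimulation off between patterns, used only to detect marker shift and prompt re-fixing. It should not be used to re-zero each pattern's joint angles. Standing posture varies from one capture to the next, so re-zeroing would add new error, and with stimulation on it could subtract a real effect on posture.

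The cost is one sentence of protocol text, slightly less comfort for subjects and a few minutes of set-up time.
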